3.3.2 Exclusion Criteria

Patients who meet any of the following exclusion criteria will not be considered eligible for this study:

1. Previous treatment with:
 - Study medication, any other JAK1 inhibitor and/or known hypersensitivity to the study medication
 - An investigational agent within 28 days prior to start of study treatment
2. Serious concurrent medical or psychiatric illness, including serious active infection
3. Uncontrolled ascites
4. Uncontrolled hypertension
5. History of organ transplant (including prior liver transplant)
6. Diagnosis of HIV, congenital immune defect, any immunosuppressive therapy for autoimmune disease or inflammatory bowel disease
7. Patients with active or latent tuberculosis
8. Patients with active hepatitis C or active hepatitis B that requires treatment
9. Patients who have received a live vaccine 30 days or fewer prior to enrolment as well as patients who intend to receive live vaccination during study participation or for three months after last dose administration
8. Patients who have a history of unprovoked venous thromboembolism (VTE) prior to the diagnosis of malignancy
9. Pregnant or breast feeding women

Other clinically significant co-morbidities that could compromise the subject's participating in the study

3.4 Procedures and Measurements

3.4.1 Visit Schedule

Patients will be seen at screening then on day 1 and day 7 of cycle 1 and then every 4 weeks (from date of day 1) in clinic whilst on treatment. Treatment will continue until disease progression. When the patients stops treatment they will be required to attend a safety follow-up visit 28 days of treatment completion. For assessment details see table 1.

Table 1: Scheduled assessments

| Time point → Assessment ↓ | Screening | Cycle 1 | | Cycle 2 | Cycle 3 | Cycle 4 | Cycle 5 | Cycle 6 - Onwards | End of Treatment ¹⁰ | Safety Follow-up |
|---|-----------------|-----------------|-----------------|---------|---------|---------|---------|-------------------------------|-----------------------------------|--------------------------------|
| | Day -28 to 0 | Day 1 Week 1 | Day 7 Week 1 | Week 4 | Week 8 | Week 12 | Week 16 | Week 20 – Every 4 Weeks | | 28 days after last dose. |
| Informed Consent | X | | | | | | | | | |
| Medical History | X | | | | | | | | | |
| Demographics | X | | | | | | | | | |
| Height | X | | | | | | | | | |
| Vital Signs ¹ | X | X | X | X | X | X | X | X | X | X |
| Physical Exam | X | X | X | X | X | X | X | X | X | X |
| ECOG Performance Status | X | X | X | X | X | X | X | X | X | X |
| ECG ⁶ | X | | | | x | | | X ⁷ | | |
| Pregnancy Test | X ¹¹ | | | X | X | X | X | X | | |
| Haematology ² | X | X | X | X | X | X | X | X | X | X |
| Biochemistry ³ | X | X | X | X | X | X | X | X | X | X |
| Serology ⁴ | X | | | | | | | | | |
| Tumour Assessments (mRECIST) ⁵ | X | | | | X | | | X ⁵ | X ⁹ | |
| Archival Tissue or Fresh Frozen Research Biopsy – Mandatory | X | | | | | | | | | |
| Research Bloods ⁸ | X | | | | X | | | X ⁸ | X | |
| ctDNA sample ⁸ | X | | | | X | | | X ⁸ | X | |
| PK Sample ⁶ | | | X | | | | | | | |
| Itacitinib administration | | X | | X | X | X | X | X | | |
| Adverse Events | | X | | | | | | | | |
| Concomitant Medications | | X | | | | | | | | |

- Vital signs include weight, blood pressure, pulse, temperature
- Haematology includes: white blood cell count (WBC) with differential, haemoglobin (Hgb), haematocrit (Hct), and platelet count
- Biochemistry includes: Chem 7 (sodium [Na], potassium [K] chloride [Cl], bicarbonate [CO₂], blood urea nitrogen [BUN], creatinine [Cr], glucose), liver function tests (LFTs - ALT, AST, alkaline phosphatase, total bilirubin, direct bilirubin), LDH, total protein, calcium, phosphate, magnesium, and cholesterol.
- Serology includes: hepatitis B surface antigen, hepatitis B surface antigen antibody, hepatitis B core antibody, hepatitis C virus antibody, HCV-RNA load, HIV serology.
- CT Scans at baseline may be performed 28 days prior to study drug administration. Subsequent tumour assessments will occur every 8 weeks from first Itacitinib dose until progression or withdrawal.
- PK Samples only applicable for the first 10 patients and should be collected on day 7 prior to first dose of Itacitinib and at 1 hour, 2 hours and 4-8 hours post dose.
- ECG every 3 cycles from first Itacitinib dose until progression or withdrawal.
- Research Bloods & ctDNA to be collected every 8 weeks from first Itacitinib dose until progression or withdrawal.
- Tumour assessment only applicable if last measurement was more than 4 weeks.
- For all patients when they finish treatment, if this is at a cycle visit then end of treatment assessments are done in place of the cycle visit assessments.
- Serum test, 14 days before first study drug administration

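### Table 1 leaves week 16 blank for tumour assessment, research bloods and ctDNA, although its own footnotes require all three every 8 weeks

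*Combined protocol and SAP*

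**What the plan says.** Section 3.4.1 brings patients to clinic "every 4 weeks (from date of day 1) in clinic whilst on treatment" and sends sites to the table for the rest: "For assessment details see table 1". Cycle 5 is the week-16 visit. The last on-treatment column, cycle 6 onwards, is headed "Week 20 – Every 4 Weeks".

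The three rows at issue are:

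- tumour assessment: "Tumour Assessments (mRECIST) ⁵ | X | | | | X | | | X ⁵ | X ⁹"
- research bloods: "Research Bloods ⁸ | X | | | | X | | | X ⁸ | X"
- ctDNA: "ctDNA sample ⁸ | X | | | | X | | | X ⁸ | X"

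Footnote 5 governs the first row: "Subsequent tumour assessments will occur every 8 weeks from first Itacitinib dose until progression or withdrawal". Footnote 8 governs the other two: "Research Bloods & ctDNA to be collected every 8 weeks from first Itacitinib dose until progression or withdrawal". The footnote markers stand on the row labels and again on the cycle 6 onwards ticks.

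Section 2.2 makes PFS a secondary endpoint that rests on mRECIST progression or death, counted from study entry. Section 4.2.3 requires study treatment to stop on clinical deterioration or progression.

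**The concern.** The ticks and the footnotes of one table give different schedules. By the footnotes, a scan, research bloods and a ctDNA sample are due at week 16. By the ticks, nothing is due between week 8 and the column that opens at week 20. No text says which takes precedence.

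A site that sets up its visit plan or case report form from the ticks would miss week 16, and a missed scan or sample cannot be recovered later. Three things depend on it:

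- **PFS dating.** Progression that only a scheduled scan would reveal is recorded late. If sites read the table differently, scan intervals would also differ between patients in a trial of 25.
- **Time on drug after progression.** Treatment runs until progression, so a patient who has progressed radiologically but not clinically could stay on itacitinib 4 to 8 weeks longer.
- **Exploratory samples.** The week-16 cytokine and ctDNA time point is lost.

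**Working it through.** The plan gives no derived figure to reproduce here. The check sets the ticks against the interval rule and then sizes the gap.

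**1. Is the blank real?** Each of the three rows has ten time-point cells, matching the ten columns, so no cell has been lost or shifted. The haematology and pregnancy-test rows, which also have ten cells, carry a tick at week 16. The visit exists and its column reads correctly.

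**2. Ticks against footnotes.** Cycle k starts at week 4(k − 1), so cycle 3 is week 8, cycle 5 is week 16, cycle 6 is week 20 and cycle 7 is week 24.

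| Week | Due by footnotes 5 and 8 | Table 1 ticks, all three rows |
|---|---|---|
| 8 | yes | ticked |
| 12 | no | blank |
| 16 | yes | **blank** |
| 20 | no | ticked (column opens, with footnote marker) |
| 24 | yes | inside the same column |

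The three rows follow the ECG row: cycle 3, then cycle 6 onwards. That pattern fits the ECG rule in footnote 7 (every 3 cycles) but not an 8-week rule. This suggests a clerical slip, though the cause is an inference.

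**3. Scan gap and dating error if week 16 is missed.**

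- Footnote: 16 − 8 = 8 weeks.
- Next scan at week 20: gap 20 − 8 = 12 weeks; progression in weeks 8 to 16 is dated 20 − 16 = 4 weeks late. Progression in weeks 16 to 20 would be dated 24 − 20 = 4 weeks earlier than under the footnote.
- Next scan at week 24: gap 24 − 8 = 16 weeks; progression in weeks 8 to 16 is dated 24 − 16 = 8 weeks late.

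These are differences between scan dates. They hold even though PFS runs from study entry and section 4.1 allows up to 28 days from enrolment to first dose.

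**4. Upper bound on patients affected.** The documents give no median PFS. Assume exponential PFS from first dose with a true median of m weeks, m between 8 and 26; every site following the ticks; and detection only at scheduled scans. Then

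expected number with an event in weeks 8 to 16 = n × (2^(−8/m) − 2^(−16/m)).

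| m (weeks) | n = 25 | n = 15 |
|---|---|---|
| 8 | 25 × (0.50 − 0.25) = 6.25 | 3.75 |
| 12 | 5.83 | 3.50 |
| 16 | 5.18 | 3.11 |
| 20 | 4.59 | 2.75 |
| 26 | 3.88 | 2.33 |

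With x = 2^(−8/m) the expression is n·x(1 − x), which is largest at x = 0.5. So 6.25 of 25 is the maximum for any exponential median, not only for the range shown.

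The n = 15 column applies if the trial stops after stage 1 with no responses (section 7.1). The probability of that is 0.95^15 = 0.463 at a true response rate of 5% and 0.75^15 = 0.013 at 25%.

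If half of these progressions were picked up before week 16 by a clinically prompted scan (also an assumption), the counts halve: 1.9 to 3.1 of 25, or 1.2 to 1.9 of 15.

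**The case against.** The strongest reply is that the schedule is already defined. Footnotes 5 and 8 are complete and mandatory, they belong to the table that section 3.4.1 points to, and their markers are on the row labels. A blank cell is an omission, not a competing rule. Either wrong reading is also strained: a next scan at week 24 applies the footnote to the cycle 6 tick but ignores it on the row label, and a next scan at week 20 ignores the count from first dose. Much of this stands. A careful site would get the schedule right, 4-weekly scanning from week 20 is not a plausible reading, and a missed week 16 is an inference about sites that work from the ticks. It does not remove the conflict, because a tick grid is what visit plans are commonly built from.

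A second reply is that the patient counts rest on assumed medians and are too high. They include deaths without earlier progression, which are dated correctly whatever the scan schedule, and they do not remove patients who left for toxicity or withdrew. That is true. Both points push the count down, so the figures remain upper bounds and should be read only as such.

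A third is that the consequence is small. Clinic visits every 4 weeks, mandatory withdrawal for clinical deterioration, and an end-of-treatment scan when the last was more than 4 weeks earlier (footnote 9) all reduce the number affected. No decision rule uses PFS, and section 7.2.1 allows translational results to stay out of the study report. This limits the weight of the point but is no reason to leave the table as it is.

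**Conclusion.** The concern holds. Table 1 contradicts its own footnotes at week 16 in three rows, and its next ticked column opens at a week that is off the 8-week grid. The footnote is probably the intent.

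The firm part of the size is the scan gap and the dating error in step 3, which need no assumption beyond a site following the ticks. The patient count is an upper bound of 3.9 to 6.25 of 25 (2.3 to 3.75 of 15), under the assumptions listed in step 4.

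The effect is limited to secondary PFS, the timing of treatment stop in patients with silent progression, and exploratory samples. The week-8 response endpoint is ticked and unaffected, and so is the two-stage rule. The table should be corrected because the contradiction is plain, the correction costs almost nothing, and the loss is permanent if a site reads it the wrong way.

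**What to change.** 1. Add a tick at cycle 5 (week 16) in the tumour-assessment, research-blood and ctDNA rows.
2. In the cycle 6 onwards column, state that these three fall at weeks 24 and 32 and every 8 weeks after that (cycles 7, 9 and every second cycle).
3. Send sites a short clarification listing the due weeks: 8, 16, 24, 32 and so on.

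The cost is three ticks, one column note and a memo. No scan or sample is added beyond what footnotes 5 and 8 already require.

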3.2 Study Flowchart

3.3 Study Population

3.3.1 Inclusion Criteria

Patients who meet all of the following inclusion criteria will be considered eligible for this study:

1. Aged 18 or over
2. Diagnosis of hepatocellular carcinoma. If primary diagnosis of HCC: diagnosis based on the following criteria:
 - cyto-histological criteria, OR
 - radiological criteria: Focal lesion >1 cm with arterial hypervascularization in 2 coincident imaging techniques (CT, MRI, or US), OR
 - combined criteria: one imaging technique showing a focal lesion 1-2 cm with arterial hypervascularization AND AFP levels >400 ng/mL, OR
 - combined criteria: one imaging technique showing a focal lesion >2 cm with arterial hypervascularization AND AFP levels >200 ng/mL
3. Progression or intolerance to first line therapy if child-Pugh A and B up to 7 points (in patients receiving anticoagulant therapy; Child-Pugh score up to 5 points; INR category not regarded for calculation of the Child-Pugh score)– N.B: Date of patients last dose of therapy must be more than 28 days before enrolment into this study
4. Child-Pugh B7 in patients who are treatment naive
5. ECOG Performance status 0, 1 or 2.
6. Adequate organ function as defined by:
 - Adequate hematologic function (ANC $\geq 1.0 \times 10^9/l$, platelet count $\geq 50 \times 10^9/l$, and hemoglobin $\geq 9g/dl$).
 - Serum creatinine concentration < 1.5 times the upper limit of normal (ULN) and/or creatinine clearance >60 ml/min
 - Bilirubin level < 1.5 X ULN
 - PT-INR/PTT < 1.5 x ULN
7. For women of child-bearing potential (defined as women who have not undergone surgical sterilization with a hysterectomy, and/or bilateral oophorectomy, and are not postmenopausal, defined as ≥ 12 months of amenorrhea) must have a negative serum pregnancy test within 14 days prior to the first study drug administration

Effective contraception must be used throughout the duration of the study and up to 30 days following

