4.2.3 Study Withdrawal

A subject **must** be withdrawn from **study treatment** IF:

- The subject has experienced an unacceptable toxicity
- The subject is unwilling to continue receiving study treatment.
- The subject has experienced clinical deterioration/disease progression.
- In the opinion of the investigator, it is in the best interest of the subject not to continue receiving the study treatment.
- The subject becomes pregnant.
- Consent to receive treatment is withdrawn.
- Termination of the study by the sponsor.
- Termination of the study by the local health authority, IRB, or IEC.

A subject **may** be withdrawn from **study treatment** if, during the course of the study:

- Is found not to have met eligibility criteria; the subject would be withdrawn if the investigator, determines that the subject would not benefit from participation in the study due to the eligibility deviation.
- Is noncompliant with study procedures or study drug administration in the opinion of the investigator.

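### When treatment finishes at a cycle visit, the Table 1 footnote drops any ECG and pregnancy test due there, because the end-of-treatment column has neither

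*Combined protocol and SAP*

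**What the plan says.** Section 3.4.1 has patients seen at screening, "then on day 1 and day 7 of cycle 1 and then every 4 weeks (from date of day 1"), which puts Cycle 2 at week 4 and Cycle 3 at week 8. The schedule is in Table 1 and its footnotes.

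- **ECG.** The row is marked at screening, Cycle 3 (week 8) and Cycle 6 onwards (week 20). It is blank at End of Treatment and Safety Follow-up. A footnote adds "ECG every 3 cycles from first Itacitinib dose until progression or withdrawal".
- **Pregnancy test.** The row reads "Pregnancy Test | X ¹¹ | | | X | X | X | X | X", and its last two cells, End of Treatment and Safety Follow-up, are blank.
- **Stopping at a visit.** The footnote attached to the End of Treatment column says that "if this is at a cycle visit then end of treatment assessments are done in place of the cycle visit assessments".
- **Tumour assessment.** "Subsequent tumour assessments will occur every 8 weeks from first Itacitinib dose until progression or withdrawal", so the first on-treatment scan is also due at week 8. Section 4.2.3 lists among the mandatory reasons to stop treatment: "The subject has experienced clinical deterioration/disease progression".
- **Contraception.** Section 3.3.1 states: "Effective contraception must be used throughout the duration of the study and up to 30 days following" the last dose.

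**The concern.** The end-of-treatment column carries over vital signs, physical examination, performance status, haematology, biochemistry, tumour assessment, research bloods and ctDNA. ECG and pregnancy test are the only repeated clinic assessments left out, and no reason is given. A rule that substitutes that column for a cycle visit therefore removes these two tests and no other repeated clinic assessment.

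Week 8 makes this more than a formality. It is the first on-treatment ECG and also the first scheduled scan, so it is a natural visit at which to find progression and stop. Safety and tolerability is a primary objective (section 2.1). An ECG change without symptoms can reach the adverse-event data only if an ECG is taken.

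For pregnancy, section 6.3.3 requires exposure to be reported to the funder, and section 1.2.2.2 reports fetal malformations in animals at the highest doses tested. Yet a patient who stops at a cycle visit has no scheduled test covering the last dosing interval.

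**Working it through.** The plan states no figure on this point, so there is none to reproduce. The check reads the two rows across Table 1's ten columns and counts the scheduled tests after screening according to which visit is run as the end-of-treatment visit. It does this once with the footnote applied and once with the tests due at that visit kept.

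| Visit run as end of treatment | ECGs, footnote applied | ECGs, due tests kept | Pregnancy tests, footnote applied | Pregnancy tests, due tests kept |
|---|---|---|---|---|
| Cycle 1 day 1 | 0 | 0 | 0 | 0 |
| Cycle 1 day 7 | 0 | 0 | 0 | 0 |
| Cycle 2, week 4 | 0 | 0 | 0 | 1 |
| Cycle 3, week 8 | 0 | 1 | 1 | 2 |
| Cycle 4, week 12 | 1 | 1 | 2 | 3 |
| Cycle 5, week 16 | 1 | 1 | 3 | 4 |
| Cycle 6, week 20 | 1 | 2 | 4 | 5 |

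Three things follow.

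1. **ECG.** Up to week 20 the footnote changes the count at two visits only: week 8 (1 becomes 0) and week 20 (2 becomes 1). Before week 8 the count is 0 either way, because no ECG is scheduled between screening and week 8 and the end-of-treatment cell is blank.
2. **Pregnancy test.** The footnote costs one test at every stopping visit from Cycle 2. Someone stopping at week 4 is left with the screening test alone.
3. **Length of the untested interval.** For a stop at Cycle 3 or later, the last scheduled test is one visit interval earlier, 4 × 7 = 28 days. For a stop at week 4 it is the screening test, which may be up to 14 days before the first dose, so up to 14 + 28 = 42 days. The safety follow-up visit, 28 days after the last dose, has no test either.

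The ECG interval note is itself unclear. The marks at Cycles 3 and 6 are three cycles apart, but three cycles counted from the first dose is 3 × 4 = 12 weeks, not 8. Neither reading places an ECG before week 8 or at end of treatment, and the week-12 reading would widen the gap.

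**The case against.** The strongest reply is that ending ECGs when treatment ends is a monitoring choice: the ECG note itself runs only to progression or withdrawal. That is consistent with a blank end-of-treatment cell, but it does not settle the matter. The tumour-assessment and research-blood notes carry the same limit, and both assessments are still marked at End of Treatment. The pregnancy-test row has no such note.

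Other parts of the reply stand:

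- **The week-8 loss is conditional.** If week 8 is run as an ordinary Cycle 3 visit and treatment stops later, for instance once the scan is read, the ECG and pregnancy test have been done. The documents do not say which applies, so sites may differ.
- **Other safety data continue.** Vital signs, examination, haematology and biochemistry are done at End of Treatment and Safety Follow-up. Adverse events are recorded, and clinically indicated ECGs are not excluded.
- **The reporting duty is not a testing duty.** Section 6.3.3 is triggered by learning of an exposure.

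A reader might be tempted to go further in four ways that the documents do not support:

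- **That the footnote strips ECGs from everyone who stops early.** It removes nothing from patients who stop before week 8, since none is scheduled for them.
- **That the co-primary safety analysis is biased towards looking safe.** Sections 2.1 and 7.2.1 plan adverse-event summaries, and no ECG endpoint or ECG summary is named.
- **That a large share of the trial is affected.** Assuming 40% to 60% stop by week 8 would give 25 × 0.40 = 10 to 25 × 0.60 = 15 patients. The documents give no stopping rate, and this count would pool patients who stop before week 8, whom the footnote does not touch, with those who stop at week 8.
- **That earlier cardiac events show an ECG risk in this trial.** In section 1.2.3 the two cardiac arrests came with a combination partner (INCB040093). The heart failure and chest pain cases were in myelofibrosis patients, apart from one heart failure case with chemotherapy. Section 1.4.2 names no ECG or conduction risk.

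**Conclusion.** The point holds as a minor gap in the schedule. As written, a patient whose week-8 visit serves as the end-of-treatment visit has no scheduled ECG after screening. A woman of child-bearing potential who stops at any cycle visit from Cycle 2 loses the pregnancy test due there, leaving 28 days since the last scheduled test, or up to 42 if she stops at week 4. These intervals assume that visits fall on schedule and that dosing runs up to the stopping visit. Patients who stop before week 8 also have no scheduled on-treatment ECG, but that comes from the schedule and the blank end-of-treatment cell.

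The consequence is incomplete safety monitoring and a pregnancy exposure that could go unnoticed. The sample size, the response-rate test and the planned adverse-event summaries are not affected. How many patients are concerned cannot be derived: the documents give no rate of stopping at cycle visits and no number of women of child-bearing potential.

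**What to change.** Reconcile the footnote with the ECG and pregnancy-test rows of Table 1: when treatment finishes at a cycle visit, the end-of-treatment assessments should be done in addition to any ECG and pregnancy test already due at that visit, not instead of them. For patients who stop between visits, the sponsor should state whether the blank end-of-treatment cells for these two tests are intended. The same edit could reconcile the ECG interval note with the week-8 mark.

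The cost is a footnote edit. The tests are already scheduled, at a visit the patient attends: no more than one ECG per patient, so at most 25, plus one pregnancy test for each woman of child-bearing potential who stops at a cycle visit. One limit remains. Section 4.2.1 permits interruptions of up to 14 days, so an ECG taken when a patient stops for toxicity may be off drug and should be labelled as such in any listing.
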